## 10.2 Adverse events

An AE is any untoward medical occurrence in a patient or clinical investigation subject administered a pharmaceutical product that does not necessarily have a causal relationship with this treatment. An AE can therefore be any unfavorable and unintended sign (including an abnormal laboratory finding), symptom, or disease temporally associated with the use of a medicinal (investigational) product, whether or not related to the medicinal (investigational) product.

AEs that occurred during the PA0008 study and are ongoing at the time of enrolment (signed informed consent) in PA0009 will be captured in the PA0009 database and followed up until the AEs have resolved, have stable sequelae, the Investigator determines that it is no longer clinically significant, or the subject is lost to follow-up.

This follow-up requirement applies to AEs, SAEs, AEs of special interest (AESI), and AEs defined as Safety Topics of Interest; further details regarding follow-up of Potential Drug-induced Liver Injury (PDILI) events are provided in the protocol Section 9.5.1. Information on SAEs obtained after clinical database lock will be captured through the Patient Safety database without limitation of time.

If an AE is ongoing at the end of the PA0009 study, follow-up should be provided until resolution/stable level of sequelae is achieved, or until the Investigator no longer deems that it is clinically significant, or until the subject is lost to follow-up. If no follow-up is provided, the Investigator must provide a justification. The follow-up will usually be continued for 20 weeks after the subject has discontinued his/her IMP.

All AEs occurring during the PA0009 study (ie, after signature of the informed consent document) will be recorded in the eCRF. For each AE the following information will be recorded in the eCRF: AE term (verbatim term), date of onset, whether or not the AE was classified as a SAE, as an AESI, intensity, relationship to study medication, action taken with study medication, other action taken, outcome, date of outcome, and whether the AE led to study drug discontinuation or to study discontinuation.

The following code lists will be used for AE recording:

- Pattern of event: intermittent or continuous.
- Intensity of event: mild, moderate or severe.
- Relationship: related or not related.

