- Action taken with IMP: dose not changed, dose reduced, dose increased, drug temporarily, interrupted, drug permanently withdrawn or not applicable.
- Outcome: resolving, not resolved, resolved, resolved with sequelae, worsened, fatal or unknown.

AEs (including SAEs) are characterized as either non-treatment-emergent or treatment emergent according to the following criteria:

- Non-treatment emergent AEs are those with onset date after a 140-day period after the end date of study medication.
  - Any AE occurring more than 140 days after the last administration of study medication in PA0008 and prior to the first administration of study medication in PA0009 will also be considered as non-treatment emergent, and will therefore be excluded from the summary tables. Such events will be included in the listings.
- TEAEs are those with onset date on or after the start date of study medication in PA0009.
- Events that were ongoing at the end of PA0008 will have their treatment-emergent status taken from the PA0008 database.

For all AEs the following variables will be calculated (see [Section 10.2.1](#)):

- Duration.
- Time since first bimekizumab dose.
- Time since last/latest bimekizumab dose.

AE summaries will, in general, include only events with onset on or after the start date of study treatment in PA0009. Certain displays will be repeated including all AEs in PA0008 (with the exception of those with onset during placebo treatment) and PA0009 as outlined below. These displays will include only subjects from PA0008 who were enrolled in PA0009.

In general, the attributes of these events (for AEs that started and were resolved in PA0008) will be taken from the PA0008 database. However, the identification of Safety Topics of Interest will be made across all events in PA0008 and PA0009 using the criteria defined in this SAP.

For events which were ongoing at the end of PA0008, the following rules will be implemented:

- Onset date (and derived variables) will be taken from the PA0008 database
- End date, outcome, actions taken and seriousness will be taken from the PA0009 database.
- In order to ensure that AEs are not duplicated in the outputs these will be merged across the studies by Subject ID, verbatim term (AETERM), dictionary-derived term (AEDECOD), start date (AESTDTC), relationship (AEREL) and severity (AESEV) to create one record for the specific event.

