Summaries of AEs in PA0008 and PA0009 combined will include AEs with onset on the first dose of bimekizumab in PA0008 up to 140 days after the last dose of bimekizumab in PA0009. AEs which occur on the day of a treatment switch will be considered to have begun on the previous treatment, with the exception of the following AEs which will be considered to have begun on the new treatment:

- Events that fulfill the anaphylaxis criteria for acute events (see [Section 10.2.3](#)).
- Events that fulfill the hypersensitivity reaction criteria for (see [Section 10.2.3](#)).
- Events with a HLT of “Administration site reactions NEC”.
- Events with an HLT of “Injection site reactions”.

AEs that occur on the first day of bimekizumab treatment in PA0008 following initial treatment with placebo will not be included in the summaries, unless they fulfill 1 of the 4 exception criteria above. AEs that occur after the last dose of bimekizumab in PA0009 and up to 140 days after the last dose of bimekizumab in PA0009 will be assigned to bimekizumab 160mg.

AEs will be presented as “number of subjects (percentage of subjects) [number of events]”. “[number of events]” will include all cases of an AE including repeat occurrences in individual subjects, while “number of subjects” will count each subject only once.

An overview of TEAE (number and percentage of subjects with any TEAE, serious TEAE, TEAE leading to study discontinuation, TEAE leading to permanent withdrawal of study medication, drug-related TEAE, severe TEAE, fatal AE [see note below], fatal TEAE and TEAE

with missing seriousness) will be provided by treatment group at completion of PA0008 and overall. This summary will be repeated by SS Sub-population.

This table will be repeated including all TEAEs in PA0008 and PA0009 reported for subjects in the PA0009 SS (with the exception of those with onset during placebo treatment) combined. The 'BKZ 160mg' treatment column in this table will include subjects in both the BKZ 160mgLD and BKZ 160mg treatment groups.

The category for fatal AEs will be based on all subjects enrolled in PA0009 in all the above summaries.

The following categories of TEAE will be summarized by MedDRA SOC, HLT and PT including EAIR and EAER (calculated as described in [Section 10.2.2](#)), where all summaries refer to AEs reported in PA0009 only except where stated:

- All TEAEs by treatment group at completion of PA0008 and overall.

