### Review Process

Opportunistic infections for a given study will be reviewed on the following occasions:

At quarterly Infectious Disease Committee (IDC) Meetings, listings will be produced for each study (see details below) and reviewed by the corresponding study physician ahead of the IDC Meeting. The IDC will then agree on the final adjudication for each potential opportunistic infection.

A final listing for opportunistic infections (in the format described below) will be produced and agreed upon between the study physician and the IDC prior to finalizing the database.

In each of the circumstances described above, the study programming team will produce an Excel listing that will be provided to the project lead statistician, project lead programmer, and to the study physician (who will subsequently provide it to the IDC). The Excel listing will contain the following columns (using the descriptions below as the column headings in the Excel listing):

- Study ID
- Unique Subject ID
- AE Term (Verbatim)
- AE Preferred Term
- AE System Organ Class
- AE High Level Term
- AE Low Level Term
- Date of Onset
- Outcome of Adverse Event

- Date of Outcome
- TEAE Flag
- Serious Adverse Event?
- Relationship to Study Medication
- Intensity
- Action Taken with IMP
- Opportunistic Infection – Automatic
- Opportunistic Infection – Manual Review
- Flag
- Data Cut Date
- Opportunistic Infection – Final Adjudication

Note the following about the final 5 variables in this listing:

Opportunistic Infection – Automatic: This is flagged as “Y” if the criteria for automatic selection as described in “Step 1” of the identification process are met.

Opportunistic Infection – Manual Review: This is flagged as “Y” if the criteria for case-by-case selection as described in “Step 2” of the identification process are met.

Flag – This has a value of either “NEW” or “OLD”. It is marked as “NEW” if the event is appearing for the first time in that run of the listing. Otherwise, if it has appeared previously, it is marked as “OLD”. Unique records are determined by USUBJID AESPID for purposes of identifying whether an event has been modified from a previous run.

Date – Only for cases where Flag is “NEW”, this field will be populated with the data cut date for that particular run of the listing.

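### The cross-study merge of ongoing PA0008 adverse events uses relationship and severity as keys, so a carried-over event re-rated in PA0009 would be counted twice in the combined outputs

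*SAP*

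**What the plan says.** SAP 10.2 says that PA0008 events which "are ongoing at the time of enrolment (signed informed consent) in PA0009 will be captured in the PA0009 database", so an ongoing event sits in both databases. For the combined outputs it sets out how the two copies become one. Onset date and the variables derived from it come from PA0008. For the rest, "End date, outcome, actions taken and seriousness will be taken from the PA0009 database". The purpose of the merge is explicit: "In order to ensure that AEs are not duplicated in the outputs these will be merged across the studies by Subject ID", followed by verbatim term, dictionary-derived term, "start date (AESTDTC), relationship (AEREL) and severity (AESEV) to create one record for the specific event". That makes six keys.

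The section does not say which database supplies relationship or severity for an ongoing event. It also does not say what happens to a pair that disagrees on one of the keys.

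The combined summaries "will include AEs with onset on the first dose of bimekizumab in PA0008 up to 140 days after the last dose of bimekizumab in PA0009". Other AE tables are narrower: "AE summaries will, in general, include only events with onset on or after the start date of study treatment in PA0009".

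**The concern.** A de-duplication key should be a field that cannot differ between two copies of the same event. Relationship and severity are judgements. The items SAP 10.2 lists for recording on the PA0009 eCRF include "intensity, relationship to study medication, action taken with study medication". A changed view of causality is plausible when a subject moves from blinded treatment in PA0008 to open-label bimekizumab in PA0009. If either rating differs, the two copies do not match under the stated rule and both remain.

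What is at stake is the event count and EAER in outputs that include PA0008 onsets, and the coherence of the listings. One event could appear as both related and unrelated. The unmatched PA0008 copy would also miss the end date, outcome, action and seriousness that the SAP intends to bring over from PA0009.

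**Working it through.** The plan states no figure on this point, so there is none to reproduce. The check applies the merge rule literally and then follows the records into the outputs.

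**1. The six-key merge on four constructed ongoing events.** All records are kept, because no rule removes an unmatched one.

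| Ongoing event | Six keys (as written) | Four keys (without relationship and severity) |
|---|---|---|
| Ratings unchanged | 1 record | 1 record |
| Causality re-rated, same start date | 2 | 1 |
| Severity corrected or lowered, same start date | 2 | 1 |
| Worsened, reported under Protocol 9.1.7 | 2 | 2 |
| Total | 7 | 5 |

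Four subjects are counted either way. The last case is correct at two records. Protocol 9.1.7 makes an increase in intensity a repeated AE whose start date is the outcome date of the first. The first record keeps its severity and still merges.

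**2. Where an extra record counts.**
- Combined TEAE and serious TEAE tables (PA0008 plus PA0009): both copies carry the PA0008 onset date and qualify. SAP 10.2 counts every occurrence in the event number, and the EAER numerator in SAP 10.2.2 includes repeats.
- Table of PA0009 TEAEs plus TEAEs ongoing from PA0008: event counts are affected. The SAP does not announce an EAER for this table.
- Combined AE and SAE listings: two entries for one event.
- Combined overview: a subject could fall in the drug-related or severe row because of the superseded copy.
- Not affected: PA0009-only tables, the number of subjects with any TEAE (each counted once), and the overall EAIR (time runs to the first occurrence, and both copies share one start date).

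**3. Size per duplicate, as an illustration.** EAER = 100 × N_AE / ΣT_Risk, so one duplicate adds 100 / ΣT_Risk. For the BKZ Total column, SAP Table 10-2 runs time at risk from the first bimekizumab dose in PA0008 to the last dose in PA0009, plus 140 days. Full follow-up is assumed:
- Bimekizumab in PA0008: 36 weeks = 252 days for subjects who started on placebo, 48 weeks = 336 days for the others.
- PA0009 dosing to Week 100: 700 days.
- 200 subjects (the maximum), lower bound: 200 × (252 + 700 + 140) / 365.25 = 597.9 subject-years; 100 / 597.9 = 0.167.
- 200 subjects, upper bound: 200 × (336 + 700 + 140) / 365.25 = 643.9 subject-years; 100 / 643.9 = 0.155.
- 100 subjects: 299.0 to 322.0 subject-years; 0.334 to 0.311 per duplicate.

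**4. Relative size.** With D duplicates among N true events, the inflation is D / N. Ten duplicates give 10 / 200 = 5% or 10 / 1000 = 1%. In the 320mg column, time at risk ends at the first PA0009 dose for subjects dosed in PA0009. That column therefore holds essentially only PA0008-onset events, and a duplicate there is not diluted by two years of PA0009 events as it is in the 160mg and Total columns.

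**The case against.** The strongest reply is that no text says the ratings of a carried-over event can be changed. The eCRF list in SAP 10.2 follows a sentence about events occurring during PA0009, so it may not cover carried-over events. Protocol 8.1 marks the recording of AEs at Visit 1 as done at PA0008 Week 48 and not needed on the PA0009 eCRF. Relationship and severity are also absent from the attributes taken from PA0009, which fits their being treated as fixed. This stands as a limit on size: the number of affected events is unknown and may be zero. It does not supply the missing source or the missing rule for mismatches. If the ratings truly are fixed, the two keys do little.

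Severity may also have a use as a key. A worsened event carries the same verbatim term as the first, and SAP 4.2.3 expects partial start dates. Two genuine events with the same month and year could then be told apart only by severity. This stands too, and the fix must allow for it.

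Three stronger readings are tempting and not supported:
- A reader might infer that every change in severity produces a false duplicate. A worsening is a separate AE under Protocol 9.1.7, so only corrections and downgrades matter.
- A reader might put a percentage on the inflation from assumed shares of ongoing and re-rated events. The documents give neither share, and zero is not excluded.
- A reader might take "Unique records are determined by USUBJID AESPID" in SAP 12.4 as proof that a cross-study identifier exists. That sentence concerns successive runs of an opportunistic-infection listing produced for each study. Nothing shows that the identifier carries over from PA0008.

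**Conclusion.** The point holds as a minor defect in specification. As written, the rule does not secure its own aim: a carried-over event whose causality is re-rated, or whose intensity is corrected or lowered with the same start date, remains as two records. Each such event adds one to the affected event counts. Assuming full follow-up, that is about 0.16 to 0.17 per 100 subject-years in the BKZ Total EAER with 200 subjects, or 0.31 to 0.33 with 100.

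A reader might conclude that the main safety results are inflated. They are not: the primary and secondary safety variables rest on PA0009-only tables. It would equally be too strong to say that no subject-level figure can change, because the drug-related and severe rows of the combined overview could. The conclusion depends on ratings being editable for carried-over events, which the documents neither state nor rule out.

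**What to change.** In SAP 10.2:
- Remove relationship and severity from the merge keys. Use a cross-study AE identifier if it is confirmed to be preserved; otherwise use subject, verbatim term, coded term and start date.
- State which database supplies relationship and severity for ongoing events. PA0009 would be consistent with the treatment of end date, outcome, actions and seriousness. The worst-case rule in SAP 4.2.3 does not settle this, since it covers only missing ratings.
- Before database lock, list and review all unmatched ongoing AEs, and any matches made on partial dates, so that a genuine worsening is not collapsed into the first event.

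The cost is a short text change, a small programming change and a brief manual check.

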### 4.2.3 Handling of missing data for adverse events

A complete date must be established to correctly identify the AE as treatment-emergent. For purposes of imputing missing components of partially reported start and stop dates for AEs, the algorithms listed below will be followed. Start and stop dates of AEs will be displayed as reported in the subject data listings (ie, no imputed values will be displayed in data listings).

Partial or missing start dates for events recorded during PA0008 (including those which were ongoing at the start of PA0009) will be imputed using the imputed start date from the PA0008 database.

Imputation of partial AE start dates for events reported in PA0009 only will follow the rules below (treatment switching rules refer to PA0008 only and data were used directly from the PA0008 database):

- If only the month and year of the AE start date are specified, and the month and year of the start date of study medication in PA0009 are not the same as the month and year of the AE start date, and the subject did not switch treatment during that month and year, then use the 1st of the month of the AE start date.
- If only the month and year of the AE start date are specified, and the month and year of the start date of study medication in PA0009 are not the same as the month and year of the AE start date, and the subject switched treatment during the month and year of the AE start date, then use the date of treatment switch.
- If only the month and year of the AE start date are specified, and the month and year of the start date of study medication in PA0009 are the same as the month and year of the AE start date, then use the start date of study medication in PA0009 (regardless of treatment switching). If this results in a start date after a known end date use the 1st of the month of the AE start date.
- If only the year of the AE start date is specified, and the year of the start date of study medication in PA0009 is not the same as the year of the AE start date, and the subject did not switch treatment during the year of the AE start date, then use the 1st of January of the year of the AE start date.
- If only the year of the AE start date is specified, and the year of the start date of study medication in PA0009 is not the same as the year of the AE start date, and the subject switched treatment during the year of the AE start date, then use the date of treatment switch.

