- If only the year of the AE start date is specified, and the year of the start date of study medication in PA0009 is the same as the year of the AE start date, then use the start date of study medication in PA0009 (regardless of treatment switching). If this results in a start date after a known end date use the 1st of January of the year of the AE start date.
- If only the year and day of the AE start date are specified, and the year of the start date of study medication in PA0009 is not the same as the year of the AE start date, then use January of the year of the AE start date together with the known day.
- If only the year and day of the AE start date are specified, and the year of the start date of study medication in PA0009 is the same as the year of the AE start date, then use the start month of study medication in PA0009 together with the known day.

- If this results in a start date after a known end date use January of the year of the AE start date together with the known day.
- If this results in a start date prior to the start date of study medication in PA0009 (in the imputed month) the event will be considered to be treatment-emergent.
- If the AE start date is completely unknown and the AE stop date is unknown or not prior to the start date of study medication in PA0009, then use the start date of study medication in PA0009.

Imputation of partial AE stop date:

- If only the month and year of the AE stop date are specified, then use the last day of that month and that year.
- If only the day and year are specified, then use December of that year
- If only the year of the AE stop date is specified, then use December 31st of that year.
- If the AE stop date is completely unknown, do not impute the stop date.

In the event of ambiguity or incomplete data which makes it impossible to determine whether the AE was treatment-emergent, the AE will be considered treatment-emergent. For subjects who may have died during the study, imputed dates will be truncated at the date of death.

If the intensity of an AE is unknown, it is considered as severe. If the relationship to study drug is missing, it is considered as related.

If the seriousness of an AE is unknown, no imputation will be performed. Such events will therefore be excluded from any listings or summaries of SAEs.

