**Table 10-2: Exposure time at risk**

Exposure Category	Start Date	End Date	Duration of Exposure
Total BKZ exposure	First dose of BKZ in PA0008	Last dose of BKZ in PA0009	Minimum of (End date – start date + 140 a ) and (Date of last clinical contact b – start date + 1)
Total exposure to BKZ 160mgLD and 160mg	First dose of BKZ 160mgLD or 160mg in PA0008 or PA0009	Last dose of BKZ 160mg in PA0009	Minimum of (End date – start date + 140 a ) and (Date of last clinical contact b – start date + 1)
Exposure to BKZ 320mg	First dose of BKZ 320mg in PA0008	First dose of BKZ 160mg in PA0009 for subjects who were dosed in PA0009 c .  Last dose of BKZ 320mg in PA0008 for subjects who were not dosed in PA0009	(End date – start date + 1) for subjects who were dosed in PA0009.  Minimum of (End date – start date + 140 a ) and (Date of last clinical contact b – start date + 1) for subjects who were not dosed in PA0009.
Exposure to BKZ 160mg in PA0009	First dose of BKZ 160mg in PA0009	Last dose of BKZ 160mg in PA0009	Minimum of (End date – start date + 140 a ) and (Date of last clinical contact b – start date + 1)

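### In the combined by-dose AE tables, PA0009-only events with onset imputed to the first PA0009 dose date count under 320mg for subjects who ended PA0008 on 320mg, even if they began on 160mg

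*SAP*

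**What the plan says.** SAP 4.2.3 defines its start-date rules by where the event was reported: "Imputation of partial AE start dates for events reported in PA0009 only will follow the rules below (treatment switching rules refer to PA0008 only"). Events already recorded in PA0008 keep the date from the PA0008 database.

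Three rules lead to the first PA0009 dose date:

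- **Day missing, month and year equal to the PA0009 start.** The instruction is "then use the start date of study medication in PA0009 (regardless of treatment switching"). The first of that month is the fallback where a known end date is earlier.
- **Year only, equal to the PA0009 start year.** The rule is the same, with 1 January as the fallback.
- **Onset wholly unknown.** "If the AE start date is completely unknown and the AE stop date is unknown or not prior to" the PA0009 start, that start date is used.

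Other partial dates go elsewhere. For a non-matching month, "and the subject did not switch treatment during that month and year, then use the 1st of the month of the AE start date". A non-matching year goes to 1 January of that year. A known day with a missing month is placed in an assigned month.

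SAP 10.2 makes an event on the first dose day treatment-emergent in PA0009: "TEAEs are those with onset date on or after the start date of study medication in PA0009". For the combined PA0008 and PA0009 summaries it adds the switch-day rule: "AEs which occur on the day of a treatment switch will be considered to have begun on the previous treatment". Four types go to the new treatment instead: acute anaphylaxis, hypersensitivity, and the administration-site and injection-site high level terms. Table 10-2 ends time at risk on 320mg at "First dose of BKZ 160mg in PA0009 for subjects who were dosed in PA0009".

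**The concern.** The switch-day rule makes sense for an event observed on the day the dose changes: it is more plausibly due to the treatment already on board. An imputed date carries no such observation. It is a placeholder that makes an undated or loosely dated event PA0009 treatment-emergent. When the placeholder falls on the switch day, the second rule moves the event back to 320mg.

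The tables affected are the combined TEAE and serious TEAE tables by treatment at onset, and the matching overview. Within this SAP they are where AE rates are shown by the dose being taken at onset. For events that truly began in PA0009 the error runs only one way, toward 320mg, which has the shorter time at risk.

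**Working it through.** The documents give no figure on this point, so there is none to reproduce. The check traces the rules and then sizes the effect under stated assumptions.

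**1. Is PA0009 entry a switch day?** SAP 10.2 does not define a treatment switch. Table 10-2 computes 320mg time at risk as end date minus start date plus 1, with the first PA0009 160mg dose as the end date, so that day is counted in 320mg time. SAP 3.7 has the 320mg and PA0009 160mg periods contribute to separate columns. The remark in SAP 4.2.3 that switching refers to PA0008 governs the imputation branches. Reading entry as the 320-to-160mg switch is therefore the natural one. Table 3-2 shows three of the seven sequences going from 320mg to 160mg; in the other four the dose does not change.

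**2. Tracing cases.** Take a 320mg completer with first PA0009 dose on 15 March 2018 (illustrative), no overriding end date and no excepted reaction:

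| Recorded onset | True onset | Imputed onset | Combined-table column |
|---|---|---|---|
| March 2018 | 28 Mar 2018 | 15 Mar 2018 | 320mg |
| June 2018 | 10 Jun 2018 | 1 Jun 2018 | 160mg |
| 2018 | 10 Nov 2018 | 15 Mar 2018 | 320mg |
| 2019 | 10 Nov 2019 | 1 Jan 2019 | 160mg |
| Unknown | 5 May 2019 | 15 Mar 2018 | 320mg |

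**3. Share charged to 320mg when onset was truly after the first 160mg dose.** Assumptions, not in the documents: onset uniform over 700 days (100 weeks) or 840 days (adding 140 days at risk); entry date uniform over a calendar year.

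- Complete date: 0%
- Day missing: 2.1% (700 days) or 1.8% (840 days)
- Year only: 26.0% or 21.7%
- Wholly unknown: 100%

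The known-day, missing-month rule also charges 12.3% or 10.2% to 320mg. It mostly does so by placing onset before the first dose, which is a neighbouring problem and not the switch-day rule.

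**4. Size.** Assume 200 subjects in five equal PA0008 arms of 40, all rolling over and completing, with placebo and 16mg subjects re-allocated 1:1 to 160mg and 320mg. Then 40 + 20 + 20 = 80 subjects ever take 320mg, 40 for 48 weeks (337 days) and 40 for 36 weeks (253 days).

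- 320mg time: (40 × 337 + 40 × 253) / 365.25 = 64.6 patient-years
- Their PA0009 time: 80 × 840 / 365.25 = 184 patient-years
- At equal event rates, 1% of PA0009 events moved: 0.01 × 184 / 64.6 = 2.8% added to the 320mg event count

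An imputed share of 0.5% to 3% would give about 1.4% to 8.5%, but the documents offer no basis for choosing a share.

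**5. On the rate scale.** One moved event per 100 subjects adds 1 / 0.693 = 1.4 per 100 subject-years to the 320mg event rate with 36 weeks on 320mg, or 1 / 0.923 = 1.1 with 48 weeks. It removes 1 / 2.30 = 0.4 from 160mg, using PA0009 time only.

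**The case against.** The strongest reply is that being reported only in PA0009 does not prove onset on 160mg. PA0009 AE collection starts at consent, before dosing, so an event dated only to the start month or year may have begun on 320mg, and for it the 320mg column is right. This stands in part. It rules out calling every such assignment an error. It is weakened because AEs are prompted at each visit, the entry AE record comes from PA0008 Week 48, and events recorded in PA0008 keep their PA0008 date. What remains are events not captured in PA0008.

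A second reply is that few events will be involved. Onset date is an eCRF field. At the 700-day shares above, reaching 1% of PA0009 events would take about 48% of events lacking a day (1 / 2.1), or about 3.8% dated by year only (1 / 26.0), or 1% wholly undated. This stands, and the 2.8% is a scaling factor, not an estimate.

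A third is that a switch is undefined and Table 10-2 also starts 160mg time on the same day. That is true, so the reading is an inference, though the better-supported one.

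Finally, the study is single-arm and descriptive. The PA0009-only tables and the BKZ Total column do not change, and listings show dates as reported, so affected events can be found.

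**Conclusion.** The point holds within limits. SAP 4.2.3 and SAP 10.2 together place some PA0009-only events under 320mg in the combined by-dose tables although they began on 160mg. It applies to 320mg completers, to the three imputation cases, and to events outside the four exceptions. The number is unknown and probably small. The figure of about 2.8% per 1% imputed rests on equal arms, full rollover and completion, equal event rates, true onset on 160mg and no excepted reactions. This is a minor correction to descriptive tables.

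Three stronger readings are tempting but unsupported:

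- **That every partial onset date is affected.** Later months and later years are imputed into the 160mg period, and a known earlier end date overrides the matching-month and matching-year cases.
- **That the PA0009-only tables already assign these events to 160mg and so contradict the combined tables.** SAP 3.7 presents PA0009-only safety summaries by treatment group at completion of PA0008, so a 320mg completer's PA0009 events sit in the BKZ 320mg column there too, with a different meaning.
- **That the change has no downside.** Some month- or year-matched events may truly have begun on 320mg.

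**What to change.** In SAP 10.2, state that the switch-day rule applies only to AEs with a complete recorded onset date. Assign AEs reported only in PA0009 whose onset is imputed to the first PA0009 dose date to BKZ 160mg in the combined by-dose tables. This follows the purpose of the imputation, which treats them as PA0009 treatment-emergent. Footnote the number of such events in each affected table. It would help to say in the same place that PA0009 entry counts as a treatment switch for 320mg completers, and to state the column for events whose missing month is imputed to before the first dose.

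The cost is a sentence or two in the SAP, one programming condition and a footnote. The downside is that a few events that began on 320mg before the first PA0009 dose would be counted under 160mg; the footnoted count lets readers judge how much that could matter.
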